11.3 Power and Sample Size

Power calculations were performed using PASS 13. When accounting for competing risks, a one-sided logrank test with an overall sample size of 102 subjects (51 in the control group and 51 in the treatment group) achieves 80% power at a 0.2 significance level to detect a hazard ratio of 0.5251. The study is expected to last for 42 months with an accrual (entry) time of 36 months and a follow-up time of 6 months after the last patient is accrued. The cumulative incidence proportions at time 3 months for the event of interest are 0.18 in the control group (8/1) and 0.10 in the treatment group (8/2). The cumulative incidence proportions at time 6 months for the competing risk factors are 0.20 in the control group and 0.20 in the treatment group. The proportion of subjects lost to follow-up during the entire study is conservatively estimated at 0.2.

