6.2.1 Retreatment

Previous studies have shown that pain relief from radiotherapy may take several weeks to become apparent. Therefore, patients should not be re-irradiated to the same treatment site for at least 4 weeks after completion of treatment on this study unless the patient has an increase of 2 points on the worst pain score above the nadir or a 25% increase in daily dosage morphine equivalent of pain medication. Dose and fractionation schemes are left to the discretion of the treating radiation oncologist. Cumulative retreatment occurrence will be recorded at the 6 month follow-up visit.

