11.5 Estimated Study Length

Since the primary analysis is based on 6 month re-treatment rates and we specify 6-months of follow-up for all patients, the protocol should be completed in 24months.

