 HR is the hazard ratio (hev2/hev1), the treatment group's hazard rate divided by the control group's hazard rate for the event of interest.
 Fev1 and Fev2 are the cumulative incidences at time T0 for the event of interest in the control and treatment groups, respectively.
 Fcr1 and Fcr2 are the cumulative incidences at time T0 for the competing risk factors in the control and treatment groups, respectively.
 R is the accrual or entry time for the study.
 T-R is the followup time for the study. T is the total time.
 Alpha is the probability of rejecting a true null hypothesis. It should be small.
 Beta is the probability of accepting a false null hypothesis. It should be small.
 E is the total number of events required for the study.
 E1 and E2 are the number of events required for the control and treatment groups, respectively.
 Pr(ev) is the overall probability of observing the event of interest during the study.
 Pr(ev1) and Pr(ev2) are the probability of observing the event of interest in a subject during the study for the control and treatment groups, respectively.
 hev1 and hev2 are the hazard rates for the event of interest in the control and treatment groups, respectively.
 hcr1 and hcr2 are the hazard rates for the competing risk factors in the control and treatment groups, respectively.
 Rpt Row is a line number assigned to allow corresponding report lines to be identified.

2/23/2016 10:03:19 AM 2

Logrank Tests Accounting for Competing Risks

Summary Statements

When accounting for competing risks, a one-sided logrank test with an overall sample size of 102 subjects (51 in the control group and 51 in the treatment group) achieves 80.195% power at a 0.200 significance level to detect a hazard ratio of 0.5251. The study lasts for 24 time periods with an accrual (entry) time of 18 periods and a followup time of 6 periods. The cumulative incidence proportions at time 3 for the event of interest are 0.1800 in the control group and 0.1000 in the treatment group. The cumulative incidence proportions at time 3 for the competing risk factors are 0.2000 in the control group and 0.2000 in the treatment group. The proportion of subjects lost to followup during the entire study is 0.2.

Logrank Tests Accounting for Competing Risks

File View Run Procedures Tools Window Help

Reset Open Save As

Calculate

Design

Design Solve For: Sample Size

Reports

Plots

Plot Text

Test

Alternative Hypothesis: One-Sided

Power and Alpha

Power: .8

Alpha: .2

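### The stated 80% power counts re-treatments over up to 24 months per patient; with the trial's 6-month follow-up, 51 per arm gives about 71%

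*Combined protocol and SAP*

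**What the plan says.** Section 11.3 claims that 102 patients, 51 per arm, tested by a one-sided log-rank test allowing for competing risks, "achieves 80% power at a 0.2 significance level to detect a hazard ratio of 0.5251". It takes re-treatment as 18% (8 Gy x 1) against 10% (8 Gy x 2) at 3 months, and loss to follow-up as 20%. On timing it says: "The study is expected to last for 42 months with an accrual (entry) time of 36 months". On competing risks it says: "The cumulative incidence proportions at time 6 months for the competing risk factors are 0.20 in the control group".

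The PASS output under Section 11.6 is the source of the power figure ("achieves 80.195% power at a 0.200 significance level to detect a hazard ratio of 0.5251"), but its inputs differ: "The study lasts for 24 time periods with an accrual (entry) time of 18 periods and a followup time of 6 periods", and "The cumulative incidence proportions at time 3 for the competing risk factors are 0.2000 in the control group".

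The endpoint is set at 6 months in Sections 2.1, 5.1 and 11.1. Section 11.5 reads: "Since the primary analysis is based on 6 month re-treatment rates and we specify 6-months of follow-up for all patients". Section 6.2.1 adds: "Cumulative retreatment occurrence will be recorded at the 6 month follow-up visit". The calendar in Section 6.1 has no visit after the 6-month one.

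**The concern.** With accrual of 18 and follow-up of 6, the calculation keeps each patient at risk until a common closing date. The first patient contributes 24 months and the last contributes 6. Re-treatments in months 7 to 24 are therefore counted towards power, although they lie outside the endpoint and no visit is scheduled to collect them.

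Log-rank power depends on the number of events. If a sizeable share of the assumed events cannot enter the analysis, the trial does not have its stated power for its stated endpoint. A null result would then be read as coming from an 80%-powered test, which overstates the evidence against the second fraction. Section 11.3 also misdescribes its own run, so a reader cannot tell from the text which assumptions produced the 80%.

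**Working it through.** **Inputs.** From Section 11.3 and the PASS output: N = 102 (1:1), one-sided alpha 0.20 (z = 0.8416), re-treatment 0.18 vs 0.10 at month 3, loss W = 0.20. From the PASS output only: competing risk 0.20 per arm at month 3, accrual R = 18, follow-up 6.

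**Hazards.** Total hazard h = -ln(1 - Fev - Fcr)/3, split in proportion to Fev and Fcr.
- Control: h = -ln(0.62)/3 = 0.1593; event 0.0755, competing 0.0839.
- Two fractions: h = -ln(0.70)/3 = 0.1189; event 0.0396, competing 0.0793.
- HR = 0.0396/0.0755 = 0.5251 (from unrounded hazards); ln HR = -0.6443.

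These match the PASS output.

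**Reproducing the plan's 80%.** With uniform accrual, Pr(event) = (hev/h) × [1 - (exp(-6h) - exp(-24h))/(18h)]. This gives 0.4138 and 0.2660, mean 0.3399, as printed.
- Events = 102 × 0.3399 × 0.8 = 27.7. PASS prints 27.5, which is what 81 evaluable patients give: 81 × 0.3399 = 27.5.
- Power = Φ(√(E/4) × 0.6443 - 0.8416) = 80.4% at 27.7 events and 80.2% at 27.5. PASS prints 80.195%.

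The match confirms that the 80% rests on 6 to 24 months at risk per patient.

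**Same inputs, each patient stopped at 6 months.** Pr(event) = (hev/h) × (1 - exp(-6h)).
- Control: 0.4737 × (1 - 0.3844) = 0.2916.
- Two fractions: 0.3333 × (1 - 0.4900) = 0.1700.
- Events = 0.8 × 51 × (0.2916 + 0.1700) = 18.8.
- Power = Φ(√(18.8/4) × 0.6443 - 0.8416) = Φ(0.556) = 71.1%.
- HR detectable with 80% power = exp(-2 × (0.8416 + 0.8416)/√18.8) = 0.46.
- Events needed for 80% at HR 0.5251 = 4 × (1.6832)²/(0.6443)² = 27.3, so N = 27.3/(0.2308 × 0.8) ≈ 148 (about 118 with no loss).

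Freedman's formula gives 69.5%. Log-rank simulations gave 70% and 73%; the 73% run spread the loss over the six months and so kept 21.5 events.

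**Sensitivity.**

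| Scenario | Events | Power |
|---|---|---|
| 6 months, 20% loss | 18.8 | 71.1% |
| 6 months, no loss | 23.5 | 76.5% |
| 6 months, competing risk 0.20 at month 6, 20% loss | 19.8 | 72.2% |
| As above, no loss | 24.8 | 77.5% |
| Every patient followed to week 34, 20% loss | 22.0 | 74.8% |
| Every patient followed to week 34, no loss | 27.5 | 80.2% |
| 18% vs 10% taken as 6-month rates, 20% loss | 11.4 | 59.8% |

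**Text against printed run.**

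| Item | Section 11.3 text | PASS run |
|---|---|---|
| Accrual | 36 months | 18 |
| Total length | 42 months | 24 |
| Competing risk 0.20 at | 6 months | 3 |

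Changing only the accrual to 36 months gives 82.3%. Entering everything as the text describes gives 86.8%. So the text does not yield 80% either, and it would count up to 42 months per patient. Section 11.5 still gives 24 months for completion, although Section 11.4 needs about 36 for accrual alone.

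**The case against.** The arithmetic is not in dispute. The case on the other side concerns how large and how certain the shortfall is.

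- **Follow-up is not strictly capped.** Section 6.4 speaks of at least 6 months, the 6-month visit may fall as late as week 34, and Appendix J asks for the date of first re-treatment without a cut-off. This softens the point. Even so, with every patient followed to week 34, power at the planned loss is 74.8%. It reaches 80% only if loss is also zero, which contradicts the plan.
- **Applying the full 20% loss to 6 months is harsh.** The plan defines it over the whole study. Assuming a constant loss rate over a mean of 15 months at risk, the 6-month loss would be 1 - 0.8^(6/15) = 8.5%. That gives about 21.5 events and 74% power. This is a fair reading, and still short of 80%.
- **The 60% figure is a different question.** Sections 1.0 and 11.3 place the 18% at 3 months. Section 11.1 quotes it without a time point beside the 6-month endpoint, and the interim calculation uses 0.2 vs 0.1, so the scenario has some support. It does not follow from the length of follow-up, however, and should be kept apart from the 71% to 76% range.
- **This is a phase II screening design at alpha 0.2.** The endpoint, the test, the type I error and the interval estimates are unaffected. That limits the harm, but the power claim remains wrong.

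**Conclusion.** The concern holds. The 80% is reproduced only by counting re-treatments over 6 to 24 months per patient. For the 6-month endpoint, with the plan's own hazards and 20% loss, the expectation is about 19 events and 71% power, so the type II error is about 29% instead of 20%. Power rises to 76% with no loss, or 77.5% if the competing risk is also 0.20 at month 6. It falls to 60% if 18% and 10% are 6-month rates. No reading that keeps 6 months of follow-up and the planned 20% loss restores 80%.

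These figures assume constant hazards, as the PASS run does, and are good to within two or three points given the spread between formulas and simulations. The disagreement between Section 11.3 and the printed run on accrual, study length and competing-risk time point needs no assumption.

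**What to change.** Rerun the calculation with a fixed 6-month observation period per patient and restate Section 11.3:

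- about 19 events expected and about 71% power for HR 0.525 at one-sided alpha 0.2 with 102 patients or, equivalently, 80% power for HR about 0.46;
- the implied 6-month re-treatment incidences, about 29% vs 17%;
- whether 18% and 10% are 3-month or 6-month rates, and over what period the 20% loss applies;
- accrual time, study length and competing-risk time point that agree across Sections 11.3, 11.4, 11.5 and the new output.

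The cost is one new PASS run, some rewording and a less favourable power figure. Stating the power correctly needs no extra patients. Keeping 80% power at HR 0.525 would take about 148 patients at 20% loss, or about 118 with none; the sponsor should make that choice with the corrected figure in view.

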11.4 Estimated Accrual Rate

It is anticipated that 3 patients a month will be accrued to this trial, thus the target of 102 patients should be met in approximately 36 months.

11.5 Estimated Study Length

Since the primary analysis is based on 6 month re-treatment rates and we specify 6-months of follow-up for all patients, the protocol should be completed in 24months.

11.6 Interim Analysis Plan

An interim futility analysis is planned for this study. After 50 patients are enrolled (25 in each group) a test statistic will be calculated for z-test to compare groups using a two-proportion test. If the test statistic has a value of 1.5 (or larger) suggesting that there is evidence that the 8/2 group has a re-treatment rate that is worse than the 8/1 group, the trial will be considered to be stopped for futility. The conditional power, if this were to occur, would be 3.5%, suggesting the futility index would be 96.5%. This calculation was performed using PASS 13.

A Prospective Randomized Phase II Study of 1 vs 2 Fractions of
 Palliative Radiation Therapy for Patients with Symptomatic Bone Metastasis
 Comprehensive Cancer Center of Wake Forest University (CCCWFU)
 CCCWFU # 01416

Logrank Tests Accounting for Competing Risks

Numeric Results for a One-Sided Test with T0 = 3 and W = 0.2

Power	N	Ctrl	Trt	Ctrl		Trt		Ctrl		Trt		Follow		
				Prop	Hazard	Main	Main	Comp	Comp	Risks	Accr1	Up		
						Event	Event	Risks	Risks	Incid	Incid	Incid	Time	Time
0.80195	102	51	51	0.5	0.5251	0.1800	0.1000	0.2000	0.2000	0.2000	18	6	0.200	1

Numeric Results for a One-Sided Test with T0 = 3 and W = 0.2 (Continued)

Beta	E	Ctrl	Trt	Ctrl		Trt		Ctrl		Trt		Comp				
				Total	Prob	Event	Event	Prob	Hazard	Event	Event	Risks	Hazard	Rate	Rate	Rpt
0.19805	27.5	16.8	10.8	0.3399	0.4138	0.2660	0.2660	0.0755	0.0755	0.0396	0.0396	0.0839	0.0839	0.0793	1	

References

 Pintilie, M., 2006. Competing Risks: A Practical Perspective. John Wiley & Sons, Chichester, United Kingdom.
 Pintilie, M., 2002. Dealing with Competing Risks: Testing Covariates and Calculating Sample Size. Statistics in Medicine, Volume 21, pages 331-7-3324.

Report Definitions

T0 is the base time at which the cumulative incidences are calculated.
 W is the proportion of the individuals lost to followup during the entire study.
 Power is the probability of rejecting a false null hypothesis. Power should be close to one.
 N is the total sample size of both groups combined.
 N1 and N2 are the sample sizes for the control and treatment groups, respectively.
 p1 is the proportion of the total sample size (N) that is assigned to the control group.
 HR is the hazard ratio (hev2/hev1), the treatment group's hazard rate divided by the control group's hazard rate for the event of interest.
 Fev1 and Fev2 are the cumulative incidences at time T0 for the event of interest in the control and treatment groups, respectively.
 Fcr1 and Fcr2 are the cumulative incidences at time T0 for the competing risk factors in the control and treatment groups, respectively.
 R is the accrual or entry time for the study.
 T-R is the followup time for the study. T is the total time.
 Alpha is the probability of rejecting a true null hypothesis. It should be small.
 Beta is the probability of accepting a false null hypothesis. It should be small.
 E is the total number of events required for the study.
 E1 and E2 are the number of events required for the control and treatment groups, respectively.
 Pr(ev) is the overall probability of observing the event of interest during the study.
 Pr(ev1) and Pr(ev2) are the probability of observing the event of interest in a subject during the study for the control and treatment groups, respectively.
 hev1 and hev2 are the hazard rates for the event of interest in the control and treatment groups, respectively.
 hcr1 and hcr2 are the hazard rates for the competing risk factors in the control and treatment groups, respectively.
 Rpt Row is a line number assigned to allow corresponding report lines to be identified.

2/23/2016 10:03:19 AM 2

Logrank Tests Accounting for Competing Risks

Summary Statements

When accounting for competing risks, a one-sided logrank test with an overall sample size of 102 subjects (51 in the control group and 51 in the treatment group) achieves 80.195% power at a 0.200 significance level to detect a hazard ratio of 0.5251. The study lasts for 24 time periods with an accrual (entry) time of 18 periods and a followup time of 6 periods. The cumulative incidence proportions at time 3 for the event of interest are 0.1800 in the control group and 0.1000 in the treatment group. The cumulative incidence proportions at time 3 for the competing risk factors are 0.2000 in the control group and 0.2000 in the treatment group. The proportion of subjects lost to followup during the entire study is 0.2.

Logrank Tests Accounting for Competing Risks

File View Run Procedures Tools Window Help

Reset Open Save As

Calculate

Design

Design Solve For: Sample Size

Reports

Plots

Plot Text

Test

Alternative Hypothesis: One-Sided

Power and Alpha

Power: .8

Alpha: .2

Sample Size

Group Allocation: Equal (N1 = N2)

W (Proportion Lost to Follow-Up): .2

Duration

R (Accrual Time): 18

T-R (Follow-Up Time): 6

Hazard Ratio

Specify the Hazard Ratio Using: Cumulative Incidences

T0 (Fixed Time Point): 3

Event of Interest - Cumulative Incidences at Time T0

Fev1(T0) (Control): .18

Fev2(T0) (Treatment): .1

Competing Risks - Cumulative Incidences at Time T0

Fcr1(T0) (Control): 0.2

Fcr2(T0) (Treatment): 0.2

Add This Procedure to Favorites List

Conditional Power Analysis of Two Proportions

Numeric Results for Conditional Power of the Two Proportion Test

Null Hypothesis: $P_1 = P_2$ Alternative Hypothesis: $P_1 > P_2$

Cond. Power	Pred. Power	Total Sample Size	Current Sample Size	Prop. Group 1	Prop. Group 2	Test Statistic	Alpha	Futility
		$N_1 N_2$	$n_1k n_2k$	P_1	P_2	Z_k		
0.03451	0.00172	51 51	25 25	0.2	0.1	1.500	0.20000	0.96549
0.02766	0.00108	51 51	25 25	0.2	0.1	1.600	0.20000	0.97234
0.02198	0.00067	51 51	25 25	0.2	0.1	1.700	0.20000	0.97802
0.01732	0.00041	51 51	25 25	0.2	0.1	1.800	0.20000	0.98268
0.01353	0.00024	51 51	25 25	0.2	0.1	1.900	0.20000	0.98647
0.01048	0.00014	51 51	25 25	0.2	0.1	2.000	0.20000	0.98952

References

Jennison, C., and Turnbull, B.W. 2000. Group Sequential Methods with Applications to Clinical Trials. Chapman & Hall/CRC. New York.
 Chang, Mark. 2008. Classical and Adaptive Clinical Trial Designs. John Wiley & Sons. Hoboken, New Jersey.

Report Definitions

Conditional Power is the probability of rejecting a false null hypothesis at the end of the study given the data that have emerged so far.

Predicted Power is the average conditional power, averaged over the effect size.

$N_1|N_2$ are the anticipated total sample sizes of groups 1 and 2.

$n_1k|n_2k$ are the sample sizes of groups 1 and 2 obtained through stage k.

P_1 is the response proportion for groups 1 and 2 under the null hypothesis.

P_2 is the response proportion for group 2 under the alternative hypothesis.

Z_k is the value of the test statistic from the observed data at stage k.

Alpha is the probability of rejecting a true null hypothesis.

Futility is one minus the conditional power. A value greater than 0.9 or 0.8 indicates the study should be stopped because there is little chance of achieving statistical significance.

Summary Statements

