4.0 Methods

4.1 Study Design

We will use a prospective randomized study design for recruiting patients with painful bone metastasis at the CCCWFU. Pain will be assessed prior to randomization. Patients will be randomized between 1 or 2 fractions of 8 Gy. The randomization will occur after registration; patients will be randomized equally between the two treatment arms. Treatment needs to begin within 14 days of registration. All baseline data needs to be collected before treatment. Quality control, such as valid values, range checks and between-variable consistency will be performed at time of data entry. Data will be kept secure with password protection.

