11.0 Statistical Considerations

11.1 Analysis of Primary Objective

This is a randomized Phase 2 study, with the primary objective to compare the 6-month cumulative incidence of re-treatment rates between groups. Based on previous research, the 8 Gy x 1 fraction [8/1] group (control group) had a retreatment rate of 18% (RTOG Study 97-14). The primary analysis will use a one-sided log-rank test statistic to test the null hypothesis that the re-treatment rates are equal in each group versus that alternative that the re-treatment rates are lower in the 8 Gy x 2 fractions [8/2] group. This analysis will account for competing risks such as death. Analyses will be performed on the patient level, thus if a patient has multiple metastases and any one of these requires retreatment then the patient will be considered retreated.

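### The futility look in section 11.6 is triggered by enrolment alone, and its 3.5% conditional power describes a different test on complete data, not the primary log-rank at that point

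*Combined protocol and SAP*

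**What the plan says.** **The look.** Section 11.6: "After 50 patients are enrolled (25 in each group) a test statistic will be calculated for z-test", comparing the arms by a two-proportion test. A value of 1.5 or more against the two-fraction arm leads to stopping being considered. The section adds: "The conditional power, if this were to occur, would be 3.5%, suggesting the futility index would be 96.5" per cent. The PASS output behind this is for the two-proportion test with 25 of 51 per arm, and defines the interim numbers only generically: they "are the sample sizes of groups 1 and 2 obtained through stage k".

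**The primary test.** Section 11.1: "The primary analysis will use a one-sided log-rank test statistic", accounting for competing risks such as death. The endpoint in section 5.1 is cumulative re-treatment at 6 months after treatment completion.

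**Timing.** Section 11.4: "It is anticipated that 3 patients a month will be accrued to this trial". The PASS summary for the log-rank design says instead: "The study lasts for 24 time periods with an accrual (entry) time of 18 periods and a followup time of 6 periods". Section 11.5, on study length, says "we specify 6-months of follow-up for all patients". Section 4.1 adds: "Treatment needs to begin within 14 days of registration". None of these ties the interim look to a length of follow-up.

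**The concern.** When the 50th patient enrols, the most recent patients have almost no follow-up and many others are short of 6 months. The rule does not say whether they count as not re-treated, are left out, or are censored. The printed conditional power avoids the question by treating all 25 per arm as fully observed, and it refers to a final test that the trial will not use. If the boundary were crossed, whoever reviews the look would read a 96.5% futility index that the rule as written does not deliver. The counting rule, which changes the answer, could then be chosen after the data are seen.

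**Working it through.** **1. Reproduce the printed figure.** Inputs (sections 11.3 and 11.6): n = 25, N = 51 per arm, one-sided alpha 0.2 (critical value 0.842), Z = 1.5. With information I = n/[2p(1−p)], p the mean of the two rates, and d their difference:

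CP = Φ{[−Z√I_k − 0.842√I_K + d(I_K − I_k)] / √(I_K − I_k)}

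At 0.18 vs 0.10, p = 0.14, I_k = 103.8, I_K = 211.8 and d = 0.08. CP = 0.03451, and the other five printed rows also reproduce (0.02766 down to 0.01048). The displayed 0.2 vs 0.1 would give 0.0505, so the table shows rounded rates. The inputs are therefore the 3-month design rates with complete outcomes.

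**2. Follow-up at the 50th enrolment.** Patients at least 6 months past enrolment:
- 3 per month: 50 − 6 × 3 = 32.
- 18-month accrual (102/18 = 5.67 per month): 50 − 6 × 5.67 = 16.

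These are upper limits, because follow-up runs from treatment completion. A 14-day lag gives about 31 and 13.

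**3. Events at the look and at the end.** The PASS hazards per month are 0.0755 and 0.0396 for re-treatment and 0.0839 and 0.0793 for competing events (control, two-fraction). Incidence by time u is (h_e/h)[1 − exp(−hu)], where h is the sum of the two hazards.
- At 6 months: 0.2916 and 0.1700. Final 6-month events: 51 × 0.4616 = 23.5, or 18.8 with 20% loss. PASS, without a 6-month cap, has 27.5.
- At the look, averaging over even accrual and capping at 6 months: 25 × (0.2474 + 0.1430) = 9.8 events at 3 per month, and 25 × (0.208 + 0.119) = 8.2 at 18-month accrual. Without the cap: 12.4 and 8.7.

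**4. Log-rank conditional power.** With information fraction t and final events E:

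CP = Φ{[−1.5√t − 0.842 + δ(1 − t)] / √(1 − t)}, δ = 0.644√(E/4), 0.644 = −ln 0.5251

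| Information fraction | E | 3 per month | 18-month accrual |
|---|---|---|---|
| 6-month events / 23.5 (t = 0.415; 0.347) | 18.8 | 10% | 16% |
| same t | 23.5 | 12% | 19% |
| same t | 27.5 | 14% | 22% |
| 6-month events / 27.5 (t = 0.355; 0.297) | 27.5 | 21% | 29% |
| uncapped events / 27.5 (t = 0.451; 0.315) | 27.5 | 11% | 26% |

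If all 50 have 6-month outcomes, t = 25/51 = 0.49 and CP is 5%, 6% and 7% for E = 18.8, 23.5 and 27.5. Missing follow-up therefore causes most of the gap. Placing the 20% competing risk at 6 months, as section 11.3 does, instead of 3 months as in the PASS run, gives 10.5-14.5%, 17.0-22.8% and 5.2-7.4% for the first three rows and the mature case, so that conflict does not change the conclusion.

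**5. Completers only.** With the formula in step 1 at Z = 1.5, 16 per arm gives 14% at 0.18/0.10 and 21% at 0.2916/0.1700. Eight per arm gives 31% and 41%.

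**6. How often the boundary is crossed under the design hazard ratio** (simulation, 300,000 trials per case): 0.6% with mature outcomes; 0.7-0.8% with partly followed patients counted as not re-treated; with completers only, 1.0% (3 per month) or 3.3% (18-month accrual).

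**The case against.** **Mature outcomes may have been intended.** Section 6.2.1 records cumulative re-treatment at the 6-month visit, the PASS run treats 25 per arm as observed, and the 50 enrolled could identify a cohort rather than a data cut. On that reading the gap is only 3.5% against 5-7%. This is plausible, but no section says it. Section 11.5 explains study length, and the PASS definition is generic software text.

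**The decision might not change.** The PASS report definitions treat an index above 0.9 or 0.8 as grounds to stop. At 3 per month, four of the five log-rank indices in the table exceed 0.8. At 18-month accrual, two of five do. This largely stands, although nearly all of them fall below 0.9.

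**Z = 1.5 exactly is the least extreme crossing.** Averaged over all crossings, with partly followed patients counted as not re-treated, simulation gives 8-10% and 13-15%. This stands, and is a reason to avoid a single replacement figure. The printed predictive power of 0.00172 does not help the plan, since it comes from the same two-proportion run on 25 complete patients per arm.

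**The larger figures rest on the 18-month accrual.** Sections 11.3 and 11.4 give 36 months. But the PASS run uses 18, and the 24-month completion in section 11.5 matches 18 + 6, so both must be shown.

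A reader might infer that the 3.5% is miscalculated. It is not: it reproduces exactly for the test it describes.

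**Conclusion.** The point holds and should be fixed, with modest practical consequence. The look has no follow-up condition, and the printed 3.5% is not the conditional power of the primary test at that look. For the log-rank it is roughly 10-21% (3 per month) or 16-29% (18-month accrual), depending on the event cap and the final event count.

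These figures assume constant hazards as in PASS, even accrual, the design hazard ratio for the remaining data and no lag to treatment. Discounting the interim events by the full 20% loss, with E = 27.5, would raise the upper ends to 31% and 37%. I leave that out of the main range because PASS defines the 20% as loss over the entire study.

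Two stronger readings are tempting and not supported. One is that a particular lower index, such as 0.88 or 0.81, is the correct one: those values rest on modelling choices that the plan does not make. The other is that the trial is likely to be stopped wrongly or its error rate inflated. The rule is advisory and futility-only, cannot raise type I error, and is crossed about 1% of the time or less under the design effect, except with completers only at 18-month accrual (3.3%).

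**What to change.** In section 11.6, define the data cut, the time point and the handling of partly followed patients. The preferred form keeps the enrolment trigger and computes the trial's competing-risk log-rank on all 50 patients, with re-treatment date and status updated to the cut. Appendix J already records the date of first re-treatment.

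Replace 3.5% and 96.5% with conditional power and futility index for the primary test at the observed event-based information fraction, stating the assumptions. First reconcile accrual (18 vs 36 months) and the time point of the 20% competing risk (3 months in the PASS run, 6 months in section 11.3).

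The alternative is to wait for 6-month outcomes on all 50. At exactly 6 months the look falls at 50 + 18 = 68 enrolled (3 per month) or 50 + 34 = 84 of 102 (18-month accrual). At the 34-week end of the visit window in section 6.1 it falls at about 74 or 94. It would then save few patients.

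Cost of the preferred form: a few sentences, one recalculation, a status check on 50 patients, and a less favourable stated index.
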